In any case, all study records are for at least 5 years after the completion or discontinuation of the study. The Investigator notified sponsor or its designee of any changes in the archival arrangements, including but not limited to archival at an off-site facility, transfer of ownership of the records in the event the Investigator left the site. Sponsor notified the Investigator in writing when the study-related records were no longer needed.

Statistical Methods Planned in the Protocol and Determination of Sample Size

The following is an outline of the statistical methodology that was used to report and analyse this study. A more detailed description is provided in a separate statistical analysis plan (SAP) that includes additional exploratory analysis not explicitly mentioned in the following sections.

Study Analyses Sets

The analyses was performed on the following trial populations.

- Randomized population: The randomized population consisted of all subjects who were randomized in the study
- Safety population: The safety population consisted of all subjects who were randomized and had received at least one dose of the IP.
- Full Analysis Population: The full analysis set population consists of all the subjects who are randomized into the study, received at least one dose of the IP from the assigned dose by randomization, and had at least one post baseline assessment.
- Per Protocol (PP) population: The per-protocol (PP) population was all the subjects in the FAS population who had completed the study and did not had any major protocol deviation.

Demographic and Other Baseline Characteristics

The demographic variables such as age, gender, ethnicity, body weight and height etc. and baseline status (medical history, physical exam, etc.) was summarized for both PP and full analysis populations.

The descriptive statistics for continuous variables were presented with number (n) of nonmissing observations, missing observations, Mean, Standard Deviation (SD), Median, Minimum and Maximum. For categorical data, descriptive statistics were presented with number of exposed subjects, and number (N) with percentage of observations in the various categories of the endpoint, where percentage were based on the exposed subjects.

Descriptive statistics were provided for body weight, waist circumference and BMI parameters. In addition, individual results were reviewed for any treatment-emergent changes of possible clinical significance.

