In this trial, safety analysis was used to perform the safety population (defined above). All safety endpoints were analysed based on descriptive statistics as described above for continuous and categorical variables and presented visit wise. The analysis of safety assessments in this study included summaries of the following categories of safety data collected for each subject.

- Adverse events (AEs)
- Physical examination
- Vital signs
- 12-lead ECG
- Laboratory investigations

Adverse Events

AEs and SAEs were coded by 20.1 version of MedDRA body system and preferred term and tabulated by indicating number and percentage of subjects and number of events. All the AEs were listed and categorized as TEAE and SAE before dosing and after dosing. All AEs, which occur after the first dose of the IP, were categorized as TEAEs i.e. AEs with onset date on or after the first dose of the IP. The TEAEs were tabulated and summarized for each treatment group as; overall TEAEs experienced by subjects during the study, TEAEs experienced by subjects during treatment with actual assigned dose of IP. All AEs were collected, evaluated and tabulated by system organ class (SOC), preferred term (PT), date of onset, relationship to the test drug, seriousness, severity, frequency, action taken, and outcome for each treatment group. Narratives of all SAEs

were presented. AE were compared between treatment groups by using Chi square/Fisher's exact test.

Vital Signs

Descriptive statistics were provided by treatment group for PR, RR, systolic and diastolic BP, and body temperature, etc. The vital signs were generated by visit as absolute values and the change from baseline were recorded. In addition, individual results were reviewed for any treatment-emergent changes of possible clinical significance.

Physical Examination

Descriptive statistics were provided by treatment group for each body system and the change from baseline were also recorded.

12-Lead Electrocardiogram

Descriptive statistics were provided. In addition, individual results were reviewed for any treatment-emergent changes of possible clinical significance.

Laboratory Assessments

Descriptive statistics were provided by treatment group for each clinical laboratory parameter and the change from baseline were also recorded. In addition, individual results were reviewed for any treatment-emergent changes of possible clinical significance.

Concomitant Medications

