
Study termination by Sponsor: Upon notification of the sponsor for termination of the study

Study termination based on the advice by CDSCO or any other competent authority: If the regulatory authority(ies) directly connects to the site/CRO to terminate the study, the same was immediately done by the Investigator/information were communicated to the sites. The CRO must notify the site regarding such communications. In case of communications directly reaching the Investigator, the Investigator must inform the CRO designee (e.g. study site monitor) or both Sponsor designee and CRO designee

Any, other reason: If none of the above-mentioned reasons are applicable, then the reason for subject withdrawal were mentioned; "any other reason" and the reason were specified on the eCRF page. In case of pregnancy, the subject's study treatment must permanently stop and study discontinuation and early withdrawal procedures should be conducted.

Determination of Sample Size

It was estimated that 52 evaluable subjects per dose group were needed to be enrolled in each treatment group assuming a reduction of 0.5 in HbA1c, common standard deviation (SD) of 1.0 at baseline and at Week 12 in each dose group with 90% power and 2.5% level of significance. However, 13 extra subjects, accounting for 65 subjects per group in total were enrolled into this study with an aim to compensate for an estimated drop-out rate of 20%. Thus, a total number of 195 subjects were to be randomly assigned to either of the three dose (treatment) groups in this study in the ratio of 1:1:1. The detailed description of sample size calculation is represented in the table below:

Single Mean - Paired t-test				
Pre-test mean	7.5			
Post-test mean	7			
Mean Difference from Pre-to Post test	0.5			
Standard deviation in Pre-test	1			
Standard deviation in Post-test	1			
Effect size	0.5			
Power (%)	90			
Alpha Error	2.5			
1 or 2 sided	2			
Minimum required sample size for each selected fixed dose treatment	52			

group	
Minimum required sample size for all three-selected fixed dose treatment	156
groups	
Considering 20% drop-out, required sample size for each selected fixed	65
dose treatment group per	
Considering 20% drop-out, required sample size for all three-selected	
fixed dose treatment groups	195

Missing Data

The missing observations were imputed using Last Observation Carried Forward (LOCF) appropriately.

Procedures for Reporting Deviations from Original Statistical Plan

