Any post-hoc, or unplanned, analyses not identified in SAP were clearly identified in the respective clinical study report (CSR).

Change in Conduct of the Study and Planned Analysis

Changes in Conduct of the Study

Following changes were made in conduct of study due to COVID-19 pandemic and nationwide lockdown implemented by Government of India:

- The home visits were arranged by investigator sites for laboratory sampling. The samples were processed in local hospital labs or central lab's local centres.
- Due to home visit physical examination and vital sign were not performed for these subjects and protocol deviations were filed.
- Telephonic contacts by the site team was done to record the AEs, concomitant medications and subject's clinical status as an alternate option to clinical visit. The participants whose blood samples were collected (hospital visit/home visit) within the one week of window period, were considered in the per-protocol population.

For site No. 20, the protocol approval was received however site initiation visit was not done because of nation-wide lockdown by the government of India due to COVID-19 Pandemic.

Change in Planned Analysis

Not applicable.

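### By-visit physical examination and ECG percentages are taken over all exposed subjects, so they are diluted by every subject not examined at that visit

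*Combined protocol and SAP*

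**What the plan says.** The denominator rule stands under Demographic and Other Baseline Characteristics, within the statistical methods. Categorical summaries show the number exposed, then counts and percentages per category, "where percentage were based on the exposed subjects". Continuous summaries are treated differently: "The descriptive statistics for continuous variables were presented with number (n) of nonmissing observations, missing observations". No number assessed or missing count is specified for categorical data.

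The Safety Analysis section carries the rule over: "All safety endpoints were analysed based on descriptive statistics as described above for continuous and categorical variables and presented visit wise". Its subsections plan descriptive statistics by body system for physical examination, and descriptive statistics for the ECG. Study Analyses Sets defines the set: "The safety population consisted of all subjects who were randomized and had received at least one dose of the IP". It requires no assessment at any given visit.

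Changes in Conduct of the Study reports, for the COVID-19 period: "Due to home visit physical examination and vital sign were not performed for these subjects and protocol deviations were filed". Change in Planned Analysis is then given as not applicable. The Missing Data section has one sentence: "The missing observations were imputed using Last Observation Carried Forward (LOCF) appropriately". It does not say whether safety data are covered.

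**The concern.** An abnormal cardiovascular examination at Visit 5 can be recorded only if somebody examined the subject at Visit 5. With a fixed exposed-subject denominator, a subject who was not examined has the same arithmetic effect on the abnormal percentage as a subject who was examined and found normal. The printed figure then mixes how often the finding occurred with how often anyone looked.

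The primary objective is to find a dose that is safe as well as effective, so readers will compare these tables across the three doses. Reasons for missing a visit can plausibly depend on dose: subjects leave for adverse events, repeated hypoglycaemia, uncontrolled hyperglycaemia or any need to change dose. If gaps are unequal, part of a difference between arms in these tables may reflect attendance and not safety.

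**Working it through.** The documents give no figure for this point that could be reproduced, so the check is the algebra of the stated rule plus illustrations.

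**Inputs from the documents**
- Denominator: exposed subjects, read here as the safety population.
- Subjects: 153 randomized 1:1:1, so 153 / 3 = 51 per arm. It is assumed that the split was exact and that all were dosed.
- Planning drop-out: 20% (Determination of Sample Size).
- Physical examination: scheduled at Visits 1 to 8, not at the dose escalation visits. ECG: scheduled at Visits 1 and 7 only.

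**Inputs that must be assumed**
- p, the rate of a finding among those examined.
- m, the share of exposed subjects not examined at the visit.

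**Formula.** With N exposed, N(1 − m) are examined and pN(1 − m) have the finding.
- Percentage on exposed = pN(1 − m) / N = p(1 − m).
- Percentage on examined = pN(1 − m) / N(1 − m) = p.

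**Range**

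| Unexamined share m | p = 10% prints as | p = 20% prints as |
|---|---|---|
| 0% | 10.0% | 20.0% |
| 10% | 9.0% | 18.0% |
| 20% | 8.0% | 16.0% |
| 30% | 7.0% | 14.0% |
| 40% | 6.0% | 12.0% |

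With examined subjects as denominator, each column stays at 10% or 20%.

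**Whole-number example, 51 exposed per arm**
- Arm with 46 examined (5 / 51 = 9.8% unexamined) and 5 findings: 5 / 46 = 10.9%, printed as 5 / 51 = 9.8%.
- Arm with 36 examined (15 / 51 = 29.4% unexamined) and 4 findings: 4 / 36 = 11.1%, printed as 4 / 51 = 7.8%.

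Near-equal rates appear as a two-point difference in favour of the arm with more gaps.

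**When the order of two arms reverses.** Arm 2, with more gaps, prints a lower percentage than arm 1 only if p2 / p1 < (1 − m1) / (1 − m2).
- m1 = 5%, m2 = 20%: 0.95 / 0.80 = 1.19.
- m1 = 5%, m2 = 30%: 0.95 / 0.70 = 1.36.
- Example with p1 = 20%, m1 = 5% and p2 = 25%, m2 = 30%: the ratio 25 / 20 = 1.25 is below 1.36, and the table shows 19.0% against 17.5%. The worse arm looks better.

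**Which planned tables are affected**
- Physical examination by body system: yes. It is categorical by nature, and home visits are a documented source of gaps.
- ECG: yes, for the investigator's interpretation as a category. Numeric ECG measurements, if summarized, would use non-missing n.
- Vital signs and laboratory values: planned as values and change from baseline, which are continuous summaries with non-missing n. No percentage table of abnormality flags is described.
- Adverse events: not affected. Exposed subjects are the right denominator for cumulative incidence.

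**Whether LOCF removes the problem.** If it does not cover safety data, the dilution stands. If it does, a missed physical examination takes the result of a preceding visit, possibly an on-treatment one. A missing Visit 7 ECG takes the pre-dose Visit 1 reading, unless the subject had an ECG at an early withdrawal visit. In either case the table would present a result from a preceding visit as if made at that visit.

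**The case against.** The strongest reply has four parts, and much of it stands.

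1. *Leaving the study is not the same as being unexamined.* The withdrawal criteria section has withdrawn subjects called in for all end-of-treatment procedures, which include physical examination and ECG. The unexamined share at Visit 7 may therefore be well below 20%, and Visit 1 is not always the only ECG available. This stands. It does not cover the intermediate visits, Visit 8, subjects who did not attend, or home visits.

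2. *Important findings are not lost.* After screening, physical examination and ECG findings judged clinically significant are recorded as adverse events. Those tables use the proper denominator and are the only safety results with a stated test between arms. This stands and limits the harm to descriptive tables.

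3. *The rule does not say that unexamined subjects are normal.* The percentage normal falls too, and the exposed number and category counts are shown, so a careful reader could recover the number assessed if every category is printed. This is fair, but the percentage is what readers compare, and no missing row is specified.

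4. *The text is an outline and refers to a separate, more detailed SAP.* That document may settle denominators. The text available states the exposed-subject rule without exception.

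A reader might also infer that the baseline tables cannot total 100%, because they are shown for the smaller PP and full analysis sets. The documents do not support this. Every subject in those sets is exposed by definition, and the natural reading is exposed subjects within the set shown.

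**Conclusion.** The point holds for by-visit categorical findings that depend on an examination: physical examination by body system and ECG category. Under the stated rule the printed percentage is p(1 − m), so a 10% rate becomes 9%, 8% or 7% at 10%, 20% or 30% unexamined. The documents establish that m exceeded zero for physical examination at some visits. They do not give m, by arm or overall, so these figures are illustrations.

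It is tempting to conclude that the arm with the most missed visits looks safest. The documents do not support that. It needs missingness that differs by arm and true rates closer than the break-even ratio (1.19 or 1.36 in the examples). Withdrawal is triggered by both low and high glucose, so even the direction across doses is unknown. It would also be wrong to say that rates at Visit 7 are understated by the planning drop-out, or in every arm: only arms with missing assessments are affected, and only to that extent.

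The conclusion rests on reading exposed subjects as the safety population, and on the separate SAP not overriding the rule. It is a defect of presentation in a trial whose objective includes safety. It is worth correcting because correction is cheap, but it does not threaten the adverse event results.

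**What to change.** Replace the single denominator rule with two, and make the table shells follow:

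- *By-visit categorical safety findings: the denominator is the number of subjects in the safety population with a non-missing assessment at that visit.*
- *Adverse event incidence: the denominator is the safety population.*

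Print the number assessed over the number exposed for each arm and visit, so that gaps from home visits and withdrawals can be seen. State that LOCF is not applied to these findings. State also whether assessments at an early withdrawal visit are tabulated under Visit 7.

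No new data are needed. The cost is a short wording change and revised shells, and some percentages become slightly less favourable. If the tables have already been produced, rerun them and identify the change in the clinical study report.

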- 25. Has any concurrent disease or medical/surgical condition, which required treatment of more than 3 months and which in the opinion of the Investigator does not allow participation of the subject in this study.

Study Specific Discontinuation/Withdrawal Criteria

The subjects could withdraw their consent to continue participation in the study without providing any reason, or the Investigator could decide in the interest of the safety of the subject to withdraw the subject from trial at any time during the study period.

The subject was withdrawn from the study treatment or discontinued from the trial due to any one of the following reason:

- Subjects' voluntary withdrawal of consent
- Protocol violation
- Subject's non-compliance to the administration of IP as per the protocol
- Any AE or SAE requiring withdrawal of subject in the opinion of the Investigator
- Requirement of prohibited concomitant medication
- Requirement of dose reduction for both IP and non-IP
- Study termination by the Sponsor
- Study termination based on the advice by CDSCO or any other competent authority
- Subjects who experience 2 or more than 2 episodes of hypoglycaemia within a day
- Subjects diagnosed with uncontrolled hyperglycaemia as defined in the protocol

The Investigator discussed with the subject, the most appropriate way to withdraw from the study to ensure the subject's health and safety. The subject was called to visit the study site and all study assessments and procedures were performed as per the EOT visit (i.e. Visit 7) (Table 3). In case of an ongoing SAE, the subjects were followed up till recovery or stabilization of SAE, whichever was appropriate without compromising on subject's safety.

STUDY TREATMENT OF SUBJECTS

Treatment Administered

- Group A: USVCAP 75 IU, BD for 12 weeks
- Group B: USVCAP 150 IU, BD for 12 weeks
- Group C: USVCAP 300 IU, BD for 12 weeks

Investigational Product

The investigational product, USVCAP was administered at doses 75 IU, 150 IU, and 300 IU, orally, twice daily.

Dosage form: It was supplied by the sponsor as 75 IU and 150 IU capsules for oral administration.

Dosage: Each subject allocated to treatment Groups A, B, or C received treatment with USVCAP IP as follows:

For subjects randomized to Group A (USVCAP 75 IU BD for 12 weeks) administered the IP as follows:

USVCAP 75 IU BD: Day 1 until Day 84

For subjects randomized to Group B (i.e. USVCAP 150 IU BD for 12 weeks) and Group C (i.e. USVCAP 300 IU BD for 12 weeks):

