Capillary glucose: Capillary glucose values of fasting > 95 mg/dL and 2 hours postprandial >126 mg/dL despite taking correct dose of study medication and regular diet was suggestive of uncontrolled hyperglycaemia. After a high capillary glucose measurement (as suggested above), subject was instructed to repeat capillary glucose measurements daily. After 03 consecutive abnormal capillary glucose measurement value, subject called the Investigator to inform above the high glucose levels and got his/her advice.

At each site visit, the Investigator reviewed the capillary glucose measurements recorded in the patient diary. If more than 60% of the capillary glucose measurement values taken since the last visit were more than the above stated value, then Investigator withdrawn the subject from the study and shifted to other hypoglycemic medication.

Plasma glucose: When, in two consecutive plasma glucose measurements, the following fasting plasma glucose (FPG) values were noted:

• From baseline to week 6 - >270 mg/dL

• From week 6 to week 12 - 240 mg/dL

Such subjects were withdrawn from the study & shifted to other anti-diabetic medication.

Prohibited Medications

The following were the prohibited medications during the study:

- Any anti-diabetic treatment other than pre-study oral monotherapy with metformin hydrochloride
- Systemic glucocorticoids and other drugs that are known to impact the glycaemic control
- Any other drug/therapy which could affect implementation of the protocol difficult or interpretation of the trial results.

Treatment Compliance

Subjects were asked to return used and unused capsules of IP at each visit. The number of unused capsules received at each visit during the treatment period (except Visit 2), including number of capsules destroyed or lost at each visit were recorded in the IP accountability log.

Compliance to study treatment at each visit was checked by reconciling the number of capsules required to be consumed and the number of capsules consumed at each corresponding visit.

Overall treatment Compliance was calculated in terms of percentage as:

 $\frac{\text{Number of tablets actually taken during the trial}}{\text{Total number of tablets to be taken during the trial}} \times 100$

Efficacy and Safety Measurements Assessment

Efficacy Assessment

Glycated Haemoglobin (HbA1c), Fasting Plasma Glucose (FPG) and Postprandial Plasma Glucose

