Capillary glucose level of < 70 mg/dL indicates hypoglycaemia. The Investigator specifically instructed the subjects to perform capillary glucose measurements in case they experienced any symptoms suggestive of hypoglycaemia. Such glucose measurements were to be preferably conducted prior to treatment/management of hypoglycaemic episode. After 15 minutes of intake of glucose tablets, repeat capillary glucose measurement was to be done to check if the capillary glucose level was >70 mg/dL. If the capillary glucose level was still <70 mg/dl, then another 04 glucose tablets was be taken and capillary glucose measurement again taken after 15 minutes. Once capillary glucose level was above 70 mg/dL, the subject was required to consume a meal or snack to prevent recurrence of hypoglycaemia.

If more than two episodes of hypoglycemia occurred within a day (despite taking correct dose of study medication and regular diet), then the subject was advised to visit the site immediately for further medical management & was withdrawn from the trial.

Uncontrolled hyperglycemia

Capillary glucose: Fasting capillary glucose values which were more than 110% of the 1st fasting capillary glucose measurement value taken in the study, despite taking the correct dose of study medication and regular diet, was suggestive of uncontrolled hyperglycaemia. After a high capillary glucose measurement (as stated above), the subject was instructed to repeat

capillary glucose measurements daily. After 03 consecutive high fasting capillary glucose measurement value, the subject called the Investigator to inform about the high glucose levels and got his/her advice.

At each site visit, the Investigator reviewed the capillary glucose measurements recorded in the patient diary. If more than 60% of the fasting capillary glucose measurement values taken since the last visit were more than 110% of the 1st fasting capillary glucose measurement value, then Investigator took fasting plasma glucose (FPG) measurements (which could be routine as per the Schedule of Study Procedures and Assessments or additional test) and then based on the fasting plasma glucose value, decided on subject withdrawal.

Plasma glucose:

Confirmed diagnosis of uncontrolled hyperglycemia were made if the following fasting plasma glucose (FPG) values are noted:

- From baseline to week 5 >250 mg/dL
- From week 6 to end of study >220 mg/dL

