Such subjects were withdrawn from the study & shifted to other anti-diabetic medication unless the fasting plasma glucose measurements were equal to or less than the 1st fasting plasma glucose measurement taken in the study.

Safety Measurements

Adverse Events

Definition of Adverse Event

As per ICH-GCP, an AE is defined as "any untoward medical occurrence in a subject or clinical investigation subject administered a pharmaceutical product and that does not necessarily have a causal relationship with this treatment". An AE can therefore be any unfavourable and unintended sign (including an abnormal laboratory finding), symptom, or disease temporally associated with the use of an IP, whether or not considered related to the IP (ICH E6: 1.2).

All abnormal laboratory findings should be classified as "clinically significant" or "nonclinically significant" by Investigator as per his clinical judgment. Only "clinically significant" abnormal laboratory values should be considered as an AE.

Worsening of a pre-existing medical condition (e.g. hypertension) during the study period should be considered as an AE, if there is either an increase in severity, frequency, or duration of the condition or an association with significantly worse outcome. Pre-existing conditions recorded at screening that have not worsened during the study period are not considered AEs.

Serious Adverse Event

An SAE is defined as an AE at any dose fulfils one or more of the following criteria:

- Results in death
- Is life-threatening*
- Requires hospitalization or prolongation of existing hospitalization*
- Results in persistent or significant disability/incapacity
- results in congenital anomaly/birth defect
- Is an important medical event: important medical event in the definition of "serious"

refers to those events which may not be immediately life-threatening, or result in death, or hospitalization, but from medical and scientific judgment may jeopardize the subject and/or may require medical or surgical intervention to prevent one of the other outcomes listed above. Examples of such events are intensive treatment in an emergency room or at home for allergic bronchospasm, blood dyscrasias or convulsions that do not result in hospitalization

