Prior and concomitant medications were coded using the standard WHODD dictionary prior to analysis. Counts and percentages were presented by drug class and generic term for descriptive summarization.

Efficacy Analyses

Primary Analysis

The primary endpoint was change in HbA1c level post 12-week administration of selected fixed dose of USVCAP (75 IU, or 150 IU or 300 IU) from baseline visit within each treatment group. The actual measurement of efficacy endpoint was summarized using number of subjects (n), mean, SD, median, and minimum and maximum (range) and 95% confidence interval (95% CI) for each treatment group at both baseline and EOT (End of treatment) visits along with change from baseline to EOT for each treatment group.

The statistical analysis for the primary endpoint were carried out to compare the change in HbA1c post 12-week administration of selected dose of USVCAP from baseline visit within each of the 3 dosing groups by using paired t-test.

In addition to evaluate primary efficacy within each randomly assigned groups as planned, we also evaluated a subgroup analysis on those patients who had uncontrolled hyperglycaemia and those who had not to see the robustness of the data on primary efficacy parameter.

Secondary Analysis

The secondary endpoint of comparing the change in HbA1c post 12-week administration of USVCAP from baseline between the 3-fixed dose groups to examine the dose response relationship between them; analysis of covariance (ANCOVA) with dose groups (treatment groups), visit and interaction between visit and treatment as factors and baseline HbA1c value as covariates using Proc mixed was used. ANCOVA model determined the statistically significant difference between different dose groups on change in HbA1c from baseline to 12-week treatment with USVCAP, controlling for the effect of the baseline HbA1c value as covariate. Also, applying same ANCOVA model and coefficient estimate for dose factor, further pairwise comparisons of the three experimental dose levels for change in HbA1c post 12-week treatment with USVCAP examined the dose response relationship.

Similarly, ANCOVA model were also applied to analyze the change in fasting and postprandial plasma glucose in each treatment group.

Details of the analysis were provided in statistical analysis plan.

Safety Analysis

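### The robustness check on the primary HbA1c result splits patients by on-treatment glucose, so neither subgroup's change can be separated from the selection that formed it

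*Combined protocol and SAP*

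**What the plan says.** The primary endpoint is the change in HbA1c from baseline to 12 weeks, tested within each dose group by a paired t-test. The Primary Analysis section then adds a "subgroup analysis on those patients who had uncontrolled hyperglycaemia and those who had not to see the robustness of the data" on the primary efficacy parameter. It gives no definition for the split and no subgroup test.

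Two sections define the state, and they differ:

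- **Subjects with inadequate glycaemic control.** The capillary rule is "Capillary glucose values of fasting > 95 mg/dL and 2 hours postprandial >126 mg/dL" despite correct dosing, with withdrawal if more than 60% of values since the last visit are above it. The plasma rule needs two consecutive fasting plasma glucose (FPG) values, above 270 mg/dL up to week 6 and then "From week 6 to week 12 - 240 mg/dL".
- **Uncontrolled hyperglycemia** (under Efficacy Assessment). The capillary rule is "Fasting capillary glucose values which were more than 110% of the 1st fasting capillary glucose measurement value taken in the study". If more than 60% exceed it, the investigator measures FPG and "then based on the fasting plasma glucose value, decided on subject withdrawal". The plasma cut-offs are above 250 mg/dL to week 5 and "From week 6 to end of study >220 mg/dL". Such subjects are withdrawn "unless the fasting plasma glucose measurements were equal to or less than the 1st fasting plasma glucose measurement taken in the study".

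HbA1c is scheduled only at Visits 1 and 7. Withdrawn subjects are called in for end-of-treatment procedures (the text reads "all study assessments and procedures were performed as per the EOT visit (i.e. Visit 7"). Missing observations are imputed by last observation carried forward (LOCF).

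**The concern.** A robustness check should vary something that could have produced the result by accident. This one sorts subjects by glucose measured while they take the product, and one version measures it against each subject's own first value. On-treatment glucose is tied to HbA1c, so the two groups can be expected to change differently even if the product does nothing. All three arms receive the product and the comparison is within arm, so nothing offsets this.

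The flagged group has a further problem. Some members leave early and contribute HbA1c from a withdrawal visit. Others stay to week 12, because the second section leaves withdrawal to an FPG decision and exempts those whose FPG is no higher than at the start. The group therefore mixes exposure times.

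At stake is how a supplementary table is read. A fall among unflagged subjects could be taken as confirmation, or a rise among flagged subjects as failure, when either may reflect the sorting.

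**Working it through.** **1. The plan's own figure.** Determination of Sample Size gives 52 per group for a paired t-test: difference 0.5, SD 1.0 before and after, effect size 0.5, two-sided 2.5%, power 90%. The normal approximation is ((2.241 + 1.282)/0.5)² = 49.6, so 50. The noncentral t gives 53, with power 89.9% at 52. The figure reproduces to within rounding. Effect size 0.5 for a difference of 0.5 means SD of change 1.0. From 1² + 1² - 2ρ = 1², the implied pre-post correlation is ρ = 0.5.

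**2. Selection formula, no drug effect.** Let p be the flagged fraction and r the correlation between HbA1c change and the glucose measure that is cut. With z = Φ⁻¹(1-p) and SD of change 1.0:

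- unflagged mean = -r·φ(z)/(1-p)
- flagged mean = +r·φ(z)/p

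Example, p = 0.20, r = 0.35: z = 0.842 and φ(z) = 0.280. Unflagged: -0.35 × 0.280/0.80 = -0.12. Flagged: 0.35 × 0.280/0.20 = +0.49. The documents give neither p nor r.

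**3. How r depends on timing.** Assume a same-time glucose-HbA1c correlation of 0.7, and a serial HbA1c correlation decaying exponentially to the implied 0.5 at 12 weeks. For a glucose level taken at week t, r(t) = 0.7 × (0.5^((12-t)/12) - 0.5^(t/12)). Using Group A's FPG calendar:

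- week 1 (Visit 3): 0.7 × (0.530 - 0.944) = -0.29
- week 2 (Visit 4): 0.7 × (0.561 - 0.891) = -0.23
- day 60, about week 8.6 (Visit 6): 0.7 × (0.820 - 0.610) = +0.15
- week 12 (Visit 7): 0.7 × (1 - 0.5) = +0.35

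An early level mainly tracks the starting HbA1c, and high starters tend to drift down. A late level mainly tracks the final HbA1c. A rise from the first value to week 12, with independent glucose error, gives r = 0.7/√(0.49 + 2 × 0.51) = 0.57.

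**4. Unflagged mean change with no drug effect, p from 5% to 40%.**

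| How the flag is formed | Unflagged mean |
|---|---|
| Rise from first value, any scheduled visit | about -0.05 to -0.23 |
| Level at week 12 only (r = 0.35) | -0.04 to -0.23 |
| Level at Visit 6 or 7 | about -0.03 to -0.18 |
| FPG cut-offs set lower later, as in both sections | about -0.02 to -0.14 |
| One fixed level, any scheduled visit | about 0.00 |
| Level at weeks 1-2 only | about +0.03 to +0.18 |

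The week-12 row uses the formula; the others are simulated under the step 3 model. If glucose error is itself serially correlated, the rise-from-first figure can reach -0.39.

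**5. If a subgroup test were run.** The documents state none. Assume a two-sided 5% paired t-test, 51 per arm (153/3) and r = 0.35. With no drug effect, simulated significant falls among unflagged subjects are about 6.5%, 12% and 24% for p = 10%, 20% and 40%, against a nominal 2.5%. The whole arm stays at about 2.5%.

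**6. The opposite error.** With a true uniform fall of 0.5, p = 10% and r = 0.35, the unflagged mean is -0.5 - 0.068 = -0.57 and the flagged mean is -0.5 + 0.614 = +0.11. A significant fall appears among flagged subjects in about 1% of simulated arms, although the drug works equally in all. The whole arm shows -0.50, significant in 94%.

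**The case against.** **The direction is not fixed.** The plasma rules are FPG levels applied from baseline onward, and early FPG tracks the starting HbA1c. This stands, as step 4 shows. A reader might infer that an inert product must produce a fall among unflagged subjects. The documents do not support that: it holds for a rise-from-first rule or late flags, not for every definition given.

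**The separate SAP may settle the definition, test and population.** This stands as a limit on what can be said about the omission. It does not rescue the split, because every definition in this document is on-treatment. *Uncontrolled on metformin* describes everyone enrolled, so it cannot form two groups.

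**Both subgroups are evaluated, and a fall among flagged subjects would run against the selection.** This is true under a rise-from-first rule or late flags, where false falls in that group are very rare. Under early flags it fails: at p = 5% and r = -0.29 the flagged mean with no drug effect is -0.29 × 0.103/0.05 = -0.60. Until the definition is known, neither subgroup's fall is evidence.

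**Penalised imputation is a separate complaint about LOCF.** This largely stands, so it is only an option in the fix.

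Two other inferences should be resisted. The primary result is not contaminated: the whole-arm test uses no flag. Nor do the documents show an undisclosed post hoc analysis. The wording sets the split beside what was planned, and Change in Planned Analysis reads as not applicable, but the unseen SAP may list it.

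**Conclusion.** The concern holds in a limited form. The split cannot serve as a robustness check, because its groups are formed on treatment by a correlate of the outcome and no control arm removes the selection. How far, and in which direction, it misleads depends on an unnamed definition. The range is about -0.03 to -0.23 for the unflagged group under a rise-from-first rule or late flags, near zero for a fixed level at any visit, and reversed for early flags only. These figures rest on SD of change 1.0 from the plan and on assumed values for the flagged fraction, the 0.7 glucose-HbA1c correlation and the serial decay. The false-fall rates also presume a test that the documents do not state. If few subjects are flagged, the effect on the unflagged group is small, but that group is then nearly the whole arm and adds little. The analysis is supplementary and severity is minor.

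**What to change.** - In the Primary Analysis section, remove the statement that this split shows robustness.
- If the split is reported, show both subgroups descriptively without p-values, with the definition used and the number in each. Label it post hoc if the SAP did not list it; Procedures for Reporting Deviations from Original Statistical Plan already commits to this.
- Reconcile the two sections that define uncontrolled hyperglycaemia. This review does not say which rule is right.
- Base the robustness statement on all full-analysis subjects in each arm. Use the HbA1c taken at the withdrawal visit, note that it may precede week 12, and report how many values are missing.
- Optionally, if hyperglycaemia withdrawals lack HbA1c, add a table replacing LOCF with unfavourable values such as screening +0.5 and +1.0. With HbA1c scheduled only at Visits 1 and 7, LOCF means a change of 0 for them, which is the reference case.

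The cost is wording changes and one extra table from existing data. The optional table shifts an arm mean by (number missing × penalty)/51. Two missing give 2 × 0.5/51 = 0.02 to 2 × 1.0/51 = 0.04, and five give 0.05 to 0.10, each towards a less favourable estimate. If withdrawal visits left few values missing, little changes.
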